A single-center prospective randomized controlled pilot trial was conducted at the Presley Regional Trauma Center at Regional One Health in Memphis, TN from 1/1/16 to 12/13/17. This hospital is the only trauma center in Memphis, serves as the only trauma center in the Mid-South area, and is a major teaching facility for the University of Tennessee Health Science Center. The Mid-South is a geographic area of approximately 3,500 square miles surrounding Memphis including western Tennessee, eastern Arkansas, northern Mississippi, and small portions of Missouri and Kentucky. The trial is registered on clinicaltrials.gov (NCT02957331). After informed consent was obtained by one of the investigators or research nurses from the patient or legally authorized representative (LAR), patients were randomly assigned to either the treatment (PRO) or control arm using block randomization in groups of 4 to ensure equal group size. This sequence was generated using SAS version 9.4 (SAS Institute, Cary, NC). The study was not blinded due to the treatment effects and need for titration of the medication on physiologic parameters.

The primary outcome was in-hospital mortality. The secondary outcome was to examine the interaction between beta-blockade and catecholamines by measuring urinary catecholamines. A power analysis was performed using literature review to determine probable effect size. Utilizing a 15% difference in mortality between groups, a sample of 99 patients per group would be required to power the study at 0.80. This sample size would not be feasible at a single center. Therefore, in lieu of performing a multi-center study with limited resources, we elected to perform a pilot study to determine study

safety, feasibility, and effect size over a one-year period. The enrollment was re-assessed after one year and still short of the goal, so the study was extended an additional year.

Eligible patients for screening were 18 years or older with a TBI as determined by Glasgow Coma Scale score (GCS) less than 12 on admission and documented brain injury on head computed tomography scan. Qualifying patients were randomized within 72 hours of injury. Exclusion criteria included patients with a significant injury in another body region (Abbreviated Injury **Scale score** >3), incarceration or gravidity, hepatic disease, home beta-blocker use, ongoing resuscitation or vasoactive medications, active acute coronary syndrome, and **non-survivable injury as determined by neurosurgery review of imaging**. Data were extracted from the electronic medical record (Sorian, Cerner, Kansas City, MO) and the local trauma registry (NTRACS version 3.0, Digital Innovations, [name]). Patients assigned to the PRO arm were dosed with propranolol starting at 20 mg three times daily (TID) by mouth or per feeding tube. The dose of propranolol was increased daily in 20 mg TID increments (60 mg/day total) until heart rate (HR) was less than 100 beats per minute (bpm) with maximum dose of 640 mg/day. Parameters for holding the medication included HR less than 60 bpm or systolic blood pressure less than 100 mm Hg. Patients assigned to the control arm were managed per institutional standard for TBI based on the Brain Trauma Foundation guidelines.²⁷ Neither arm had additional beta-blockers withheld if the care team deemed that class of medication necessary for appropriate care. Treatment duration for active study intervention was 14 days with a 48-hour taper of propranolol after the study period ended in the PRO arm. Patients were followed during the hospital stay until death or discharge.

Variables collected included demographics, severity of injury, severity of illness scores, physiologic parameters, operative interventions, hospital length of stay (LOS), intensive care unit length of stay (ICU LOS), discharge disposition, infectious morbidity, urinary catecholamines, and mortality. Urinary catecholamines were collected from discarded urine at study enrollment and then at study day (SD) 2, SD-5, SD-7, SD-10, and at the end of the study period (SD-14) or when the patient came off study. The samples were stabilized with hydrochloric acid (HCl) and sent to a standard lab. Timely acid stabilization of the urine specimens was required prior to shipping to the central lab for processing. If HCl was not added to the specimen, unpredictable results were obtained that were not physiologically possible *in vivo*. These values were excluded from analysis. Patients in the PRO arm were compared to the control **using intent to treat analysis.**

Statistical analyses for categorical variables were compared using *Chi*-square tests or Fisher's exact tests where appropriate. Normally distributed continuous variables were compared using *Student's* t-tests and non-normally distributed continuous variables were compared using Wilcoxon Rank Sums tests. Effect size for mortality was calculated using the absolute difference between treatment groups. A two-way mixed model III Analysis of the Variance (ANOVA) with repeated measures was used to estimate differences between the two treatment arms over time. Using planned contrasts, the mean for each follow-up measurement was compared to SD-1 (i.e., randomization) for *within-group* contrasts and means at each assessment time were compared for *between-group* contrasts. Because these contrasts were planned, no correction was made for multiple comparisons. Output for the ANOVA is reported as Least Square Means

(LSMeans) with standard error (\pm SE). Finally, Kaplan-Meier survival analysis was performed to further examine mortality over time between groups. All statistical analyses were performed using SAS 9.4 (SAS Institute, Cary, NC). The University of Tennessee Health Science Center and Regional One Health Institutional Review Boards approved the study. A *p* value of less than 0.05 was considered significant.

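### A single block size of 4 in an open single-center trial would let staff who knew the size and kept a tally foresee one third of assignments on average (low severity)

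*Combined protocol and SAP*

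**What the plan says.** The sections of the combined protocol and SAP are unnumbered. The opening account of design and outcomes describes one center and two arms. It says "patients were randomly assigned to either the treatment (PRO) or control arm", "using block randomization in groups of 4 to ensure equal group size", with a sequence generated in SAS. No second block size, stratification or concealment method is described, and nothing says whether enrolling staff knew the block size.

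Assignment follows consent: "After informed consent was obtained by one of the investigators or research nurses". Treatment is open: "The study was not blinded due to the treatment effects and need for titration of the medication on physiologic parameters". The account of eligibility and treatment gives titrated study drug to one arm only ("The dose of propranolol was increased daily in 20 mg TID increments") and lets patients be randomized up to 72 hours after injury.

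The account of data and analysis says: "Effect size for mortality was calculated using the absolute difference between treatment groups". No covariate adjustment of mortality is described, although severity is recorded: "Variables collected included demographics, severity of injury, severity of illness scores, physiologic parameters".

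On size, the design text says "a sample of 99 patients per group would be required to power the study at 0.80". It then calls that number infeasible at one center and turns to a pilot. The pilot has an enrollment goal, but its number is not given.

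**The concern.** With one center, one list and visible treatment, local staff can reconstruct past assignments without seeing the list. If every block holds two PRO and two control patients, a tally shows when one arm's places are used up, and the rest of that block is then known.

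Consent before assignment does not prevent this, because the discretion lies in whom to approach, and when within the 72-hour window. If that discretion followed prognosis, the arms would differ at baseline. An unadjusted difference in mortality would carry the imbalance straight into the estimate. Intent-to-treat analysis protects against exclusions after randomization, not against selective approach before it. The pilot is meant to inform on effect size, so a biased estimate could also feed into the planning of a larger trial.

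**Working it through.** **Inputs.** From the documents: block size 4, two arms, one center, open treatment. Inferred from the aim of equal groups: two PRO (P) and two control (C) places per block. Assumed: staff know the size and keep a tally. The documents state no predictability figure to reproduce.

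**Certain assignments.** A block of 4 has 6 equally likely orders.
- PPCC and CCPP: the last two places are forced, 2 of 4 (50%).
- The other four orders: only the last place is forced, 1 of 4 (25%).
- Average: (2 × 2 + 4 × 1) / (6 × 4) = 8/24 = 33.3%.
- By position: 0, 0, 1/3, 1.

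**Best guess.** Name the arm that is behind, and toss a coin at a tie. The chance of being right by position is 1/2, 2/3, 2/3, 1. The average is (17/6)/4 = 17/24 = 70.8%, against 50% under simple randomization. This rule needs only the tally, not the block size.

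**Spread of the certain share.** This depends on trial length, which the documents do not give. Taking the number of 50% blocks as binomial with probability 1/3, the 95% range is about 30% to 36% at an assumed 198 patients, 26% to 38% at an assumed 50, and 23% to 38% at an assumed 26.

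**Shift in the mortality difference.** Let *g* be the difference in mortality risk between patients enrolled at predicted-PRO and predicted-control turns. The values of *g* are assumptions.

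| *g* (points) | Acting on certain turns only: 1/3 × *g* | Acting on every best guess: (2 × 17/24 − 1) × *g* |
|---|---|---|
| 2 | 0.67 | 0.83 |
| 5 | 1.67 | 2.08 |
| 10 | 3.33 | 4.17 |

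**Yardstick.** The standard error of the difference is √{[p₁(1−p₁) + p₂(1−p₂)]/n}, with a 15-point difference and an assumed control mortality of 25% or 40%.
- n = 99 per arm: √(0.2775/99) = 5.3 points; √(0.4275/99) = 6.6 points.
- n = 25 per arm (assumed): √(0.2775/25) = 10.5 points; √(0.4275/25) = 13.1 points.

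The largest shift, 4.17, is 4.17/5.29 = 0.79 of a standard error at 99 per arm and at most 4.17/10.5 = 0.40 at 25 per arm.

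**Alternative: sizes 4, 6 and 8, equally likely.** In simulation, staff who know the set of sizes but not their order can be certain of 2.2% to 2.4% of assignments. The certain-turn shifts become about 0.023 × *g* = 0.05, 0.11 and 0.23 points. Naming the arm that is behind has an exact long-run accuracy, summing over half-block sizes b = 2, 3, 4, of Σ[b + 2^(2b−1)/C(2b,b) − 0.5]/18 = (2.833 + 4.100 + 5.329)/18 = 0.681. Simulated accuracy for sequences of 26 to 198 patients was 67.4% to 68.0%. At 0.681 the best-guess shifts are 0.362 × *g* = 0.72, 1.81 and 3.62 points, little lower than with blocks of 4.

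**The case against.** The harm needs four things in sequence: staff knew or inferred the size, tallied assignments, let the tally decide whom to approach, and did so on prognosis. The documents support none of these. A reader might infer that allocation was in fact predicted, or that silence on concealment means there was none. Neither follows: the text is silent on both, and it does place consent before assignment. Eligibility rests largely on measurable criteria, and a neurosurgical review of imaging decides which injuries are non-survivable. This narrows discretion over who is eligible, but not over who is approached or when.

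A reader might also treat 198 patients as the planned size. It is the size the authors set aside, so every figure tied to 198, 50 or 26 patients is illustrative.

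The remedy has limits too. Varying blocks nearly remove certainty but barely reduce guessing. Small fixed blocks serve a stated purpose, equal groups, which has value in a small trial that may stop mid-block. Enrollment has ended, so the randomization cannot be changed here.

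These points stand and lower the severity. They do not remove the concern, because no described safeguard acts on whom staff approach.

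**Conclusion.** The point holds as a low-severity note on design risk. Given complete 2:2 blocks of 4, a known or inferred size and a tally, 33.3% of assignments on average are certain in advance and a best guess is right 70.8% of the time. These two figures are exact under those conditions. The illustrated shifts, 0.7 to 3.3 points on certain turns and 0.8 to 4.2 on every best guess, rest on assumed risk gaps. All lie below one standard error at 99 per arm, and are a smaller fraction of it in a smaller pilot. Unlike sampling error, such a bias would not shrink as more patients are enrolled, so it matters more for a larger successor trial.

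A reader might infer that the mortality comparison is biased. The documents do not support that: they leave open whether any assignment was foreseen or acted on.

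**What to change.** **Design, or a follow-on trial.** Replace the groups of 4 with randomly varying block sizes, for example 4, 6 and 8. Keep both the sizes and the set of sizes from staff who approach and consent patients. Release each assignment only after consent and eligibility are recorded, and state who holds the list. The cost is a small change to the SAS program and a worst imbalance of 4 patients instead of 2 if enrollment stops mid-block. The plan should say that this removes nearly all certain turns but lowers best-guess accuracy only from 71% to about 67-68%.

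**This trial.** Add a sensitivity analysis of in-hospital mortality adjusted for baseline injury severity. Limit it to one or two baseline covariates, because deaths may be few, and report it beside the unadjusted difference. State how the sequence was concealed and whether enrolling staff knew the block size. No new patient data are needed. State also that adjustment cannot remove selection on unmeasured prognosis.

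### The mortality effect size ignores admission GCS, which is known for every patient; a GCS-stratified estimate would be a cheap, modest improvement

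*Combined protocol and SAP*

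**What the plan says.** All of this comes from the unnumbered methods text of the combined protocol and SAP.

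- **Eligibility.** Adults enter with "a TBI as determined by Glasgow Coma Scale score (GCS) less than 12 on admission" and a brain injury documented on CT. As 3 is the floor of the scale, this means GCS 3 to 11. The worst end is trimmed by excluding "non-survivable injury as determined by neurosurgery review of imaging".
- **Randomization.** Patients were allocated "using block randomization in groups of 4 to ensure equal group size". No stratification factor is named.
- **Primary outcome and sizing.** "The primary outcome was in-hospital mortality". On size: "Utilizing a 15% difference in mortality between groups, a sample of 99 patients per group would be required to power the study at 0.80". The text calls that number infeasible at one center and gives the pilot three purposes: safety, feasibility and effect size. It states no pilot sample size.
- **Analysis.** "Effect size for mortality was calculated using the absolute difference between treatment groups". Categorical variables are compared by Chi-square or Fisher's exact tests, and survival by Kaplan-Meier. The only model described is a repeated-measures ANOVA for differences between arms over time, which is not the mortality effect.
- **Data held.** "Variables collected included demographics, severity of injury, severity of illness scores". None of these is assigned to the mortality analysis.

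**The concern.** Admission GCS is an obvious prognostic factor for in-hospital death, and the entry range puts deep coma and moderate injury in one population. Blocks of 4 equalize the number of patients per arm, not their severity. In a small trial one arm can by chance receive noticeably more patients with low GCS, and the crude difference then reflects this as well as any treatment effect.

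What is at stake is the estimate that a follow-on trial would be built on. The crude difference alone does not show a reader whether this single randomization was tilted by severity. A GCS-stratified estimate beside it would, and it needs only a variable that every patient has by definition of eligibility.

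**Working it through.** **The plan's own figure.** The 99 per group cannot be derived from the documents, because base rates and sidedness are not stated. It is compatible with, for example, 25% against 10%, two-sided alpha 0.05 and power 0.80:

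n = [1.96 × √(2 × 0.175 × 0.825) + 0.842 × √(0.25 × 0.75 + 0.10 × 0.90)]² / 0.15² = (1.053 + 0.443)² / 0.0225 ≈ 99.5, or 100 rounded up.

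Nothing here shows 99 to be wrong. The figure used below is the 15-point effect, half of which is 7.5 points.

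**Inputs for the scenario (all assumed; none is in the documents).** n = 25 per arm; share with GCS 3-8, q = 0.60; mortality 30% or 40% in GCS 3-8 and 5% in GCS 9-11, so a gap g of 25 or 35 points; no treatment effect.

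**Step 1, imbalance in severity.** SD of the between-arm difference in the GCS 3-8 share = √(2q(1−q)/n) = √(2 × 0.6 × 0.4 / 25) = 13.9 points.

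**Step 2, effect on the mortality difference.** Shift = imbalance × g. SD = 13.9 × 0.25 = 3.5 points, or 13.9 × 0.35 = 4.8 points.

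**Step 3, total standard error of the crude difference.** Overall mortality is 0.6 × 0.30 + 0.4 × 0.05 = 0.20, or 0.6 × 0.40 + 0.4 × 0.05 = 0.26. SE = √(2 × 0.20 × 0.80 / 25) = 11.3 points, or √(2 × 0.26 × 0.74 / 25) = 12.4 points. The severity part of the variance is (3.46/11.31)² = 9%, or (4.85/12.41)² = 15%.

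**Step 4, chance of a 7.5-point shift.** The imbalance needed is 7.5/0.25 = 30 points (at least 8 of 25 patients) or 7.5/0.35 = 21.4 points (at least 6 of 25). Exact probabilities from two independent binomials, either direction:

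| Per arm (assumed) | Gap 25 points | Gap 35 points |
|---|---|---|
| 15 | 9% | 19% |
| 25 | 3% | 11% |
| 40 | 0.8% | 5% |

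An imbalance of 20 points or more is commoner (19% of trials at 25 per arm), but it moves the estimate by as little as 20 × 0.25 = 5 points or 20 × 0.35 = 7 points, short of 7.5.

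**Step 5, gain from stratifying.** Removing the severity component entirely would cut the SE by 1 − √(1 − 0.094) = 5%, or 1 − √(1 − 0.153) = 8%. Simulating the Mantel-Haenszel estimator itself at 25 per arm (400,000 trials per setting) gave an SE of 10.9 against 11.3 points, and 11.6 against 12.4 points: a reduction of about 4-7%. The 95% half-width (1.96 × SE) goes from about 22-24 points to about 21-23.

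**Step 6, sparseness.** Expected deaths in GCS 9-11 are 25 × 0.4 × 0.05 = 0.5 per arm. The chance of none in either arm is (1 − 0.4 × 0.05)^50 = 36%.

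**The case against.** The strongest reply is that nothing here is an error. Simple blocked randomization with an unadjusted risk difference is a valid and transparent analysis for a single-center pilot. Randomization keeps the estimate unbiased, and chance imbalance in severity is already inside the standard error. The imprecision comes mainly from small numbers, which the plan openly acknowledges, and stratifying removes only a few percent of it. Eligibility also narrows prognosis by excluding non-survivable injury, major injury in another body region, and ongoing resuscitation or vasoactive medication. Severity scores are collected and general comparison tests are described, so the arms could be compared on severity, although the text does not say that this is planned. Finally, the trial is described as already conducted, so its randomization cannot be changed.

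Most of this stands and limits the point to a small improvement. It does not remove the point: effect size is a stated aim, the prognostic variable is already held, and the crude figure alone does not show how far imbalance contributed.

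A reader might go further and infer that severity imbalance can be expected to move the estimate by half the assumed 15-point effect. The documents do not support that. They give no pilot size, GCS mix or mortality by GCS, and under the assumptions above such a shift is a tail event.

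**Conclusion.** The point holds as a modest one. It is fact that entry spans GCS 3 to 11, that no severity stratification is described, and that the mortality effect size is unadjusted although admission GCS is known for all.

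The size is a scenario only. With the assumed inputs above, the severity component (SD 3.5-4.8 points) accounts for about 9-15% of the variance of the crude difference, and a shift of 7.5 points or more is an occasional event (about 3-11% of trials). The likelihood rises with fewer patients or a wider mortality gap, and falls with more patients.

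It would be wrong to read the crude estimate as biased, or the imbalance as an error on top of its standard error. The main benefit of stratifying is a more interpretable single estimate; the gain in precision is small.

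**What to change.** - **This trial.** Report a Mantel-Haenszel risk difference for in-hospital mortality stratified by admission GCS (3-8 versus 9-11), with a confidence interval, beside the crude difference. If it was not prespecified, label it as an added analysis.
- **Any follow-on trial.** Run the randomization blocks within the same two GCS strata and prespecify the stratified estimate.

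**Cost.** One further analysis on data already held and, later, one more level in the randomization list. The drawback is that deaths in the GCS 9-11 stratum may be few or absent, so the gain in precision is modest. For that reason a single two-level factor is enough.

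### The catecholamine model takes no account of hours from injury to randomization, which can range up to 72, so its unbiased between-arm contrasts may carry variance that one covariate would remove.

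*Combined protocol and SAP*

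**What the plan says.** All references are to the combined protocol and SAP, whose methods text has no numbered sections.

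- **Eligibility and treatment paragraph:** "Qualifying patients were randomized within 72 hours of injury".
- **Design paragraph:** allocation used "block randomization in groups of 4 to ensure equal group size". No stratification by time since injury is stated. Urinary catecholamines are the only named secondary outcome.
- **Variables paragraph:** "Urinary catecholamines were collected from discarded urine at study enrollment and then at study day (SD) 2", and again on days 5, 7, 10 and 14 or when the patient came off study. Hours from injury to randomization are not among the variables listed.
- **Statistical analysis paragraph:** a two-way mixed ANOVA "with repeated measures was used to estimate differences between the two treatment arms over time". Within arms, "the mean for each follow-up measurement was compared to SD-1 (i.e., randomization) for *within-group* contrasts". Between arms, "means at each assessment time were compared for *between-group* contrasts". No covariate and no transformation of the catecholamine values are named.

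**The concern.** Two patients on the same study day can be up to three days apart in their post-injury course. If catecholamine levels depend on time since injury, part of the between-patient spread on each study day is simply enrollment delay. Delay is fixed before allocation and could be used as a baseline covariate, but the model leaves its contribution in the error term. The pilot fell short of its enrollment goal after one year, and some urine values were excluded for want of acid stabilization, so precision on this outcome matters. A separate limit applies to the planned within-arm contrasts: a fall from SD-1 in the propranolol arm could be drug effect, natural course, or both.

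**Working it through.** The plan gives no figure on this point. Its one design calculation, 99 per group, concerns mortality and is not used here.

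**Step 1. Time windows (from the documents alone).** Taking SD-1 as randomization and entry at 0 to 72 hours, study day d covers 24(d − 1) to 24(d − 1) + 72 hours after injury:

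| Study day | Hours after injury |
|---|---|
| SD-1 | 0–72 |
| SD-2 | 24–96 |
| SD-5 | 96–168 |
| SD-7 | 144–216 |
| SD-10 | 216–288 |
| SD-14 | 312–384 |

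The SD-1 and SD-2 windows share 72 − 24 = 48 hours, so one patient's SD-1 sample can be later after injury than another's SD-2 sample. From SD-5 on there is no overlap with SD-1, but every day still spans 72 hours.

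**Step 2. Assumptions for size (none is in the documents).** Levels fall exponentially after injury with half-life h of 2 to 3 days (wider range 1.5 to 5). Entry is uniform over 0 to 3 days. Residual between-patient log-SD r is 0.5 to 0.8. There are n = 25 patients per arm. The analysis is on the log scale.

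**Step 3. Spread due to delay.** With k = ln 2 / h and the SD of a uniform(0, 3 days) variable equal to 3/√12 = 0.866 days, the log-SD due to delay is s = 0.866k.

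- h = 2: k = 0.347, s = 0.300.
- h = 3: k = 0.231, s = 0.200.

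**Step 4. Standard error of a between-arm contrast on one study day.** Unadjusted: √(s² + r²) × √(2/n). With delay fully removed: r × √(2/n). Here √(2/25) = 0.283.

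| h (days) | r | Unadjusted SE | Adjusted SE | Reduction |
|---|---|---|---|---|
| 2 | 0.5 | 0.165 | 0.141 | 14% |
| 3 | 0.5 | 0.152 | 0.141 | 7% |
| 2 | 0.8 | 0.242 | 0.226 | 6% |
| 3 | 0.8 | 0.233 | 0.226 | 3% |

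Apart from the lost degree of freedom, the percentage reduction is 1 − r/√(s² + r²) and does not depend on n.

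**Step 5. Sensitivity.**

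- Half-life 5 days: s = 0.120, and the reduction is 1% (r = 0.8) to 3% (r = 0.5).
- Half-life 1.5 days: s = 0.400, and the reduction is 11% (r = 0.8) to 22% (r = 0.5).
- Entry uniform over 24 to 72 hours, half-life 2 to 3 days: SD of entry = 2/√12 = 0.577 days, s = 0.133 to 0.200, and the reduction is 1% to 7%.

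**Step 6. Bias.** Allocation is random, so expected delay is equal in the two arms. A simulation of exponential decline on the raw scale, with uniform entry and 30 per arm, gave a mean between-arm difference of about 0 for half-lives of 48, 72 and 120 hours.

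**Step 7. Within-patient change.** On the log scale, a patient entering at time T has level −k(T + d − 1) on day d, with T and d in days, relative to the level at injury. The change from SD-1 is −k(d − 1), so T cancels. On the raw scale it does not cancel: with a 72-hour half-life, the SD-2 minus SD-1 change is −0.21 of the level at injury for entry at 0 hours and −0.10 for entry at 72 hours.

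**The case against.** **The premise is outside the documents.** No section describes how catecholamines move after injury, and the half-life, entry pattern, residual spread and arm size are all assumed. Half-lives of 2 to 3 days imply a fall of 2^(13/3) to 2^(13/2), roughly 20- to 90-fold, by SD-14, which nothing in the text supports. Entry in the first hours is also less likely, because CT and consent came first and ongoing resuscitation or vasoactive drugs excluded a patient. This stands: the size is conditional, and the wide-entry figures are probably near the upper end.

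**Study day is the right index.** Propranolol was titrated daily from randomization, so study day also tracks treatment exposure, and indexing by day since injury would mix exposure stages instead. This stands. A reader might infer that the clock is wrong, but the documents do not support that.

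**Chance imbalance is already in the standard error.** This also stands. A reader might infer that the between-arm contrasts are biased by uneven delay. Randomization rules out systematic bias, and chance imbalance is the same thing as the extra variance, not a second defect.

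**Within-arm change need not depend on delay.** A reader might infer that it does. Under exponential decline on the log scale, delay cancels exactly and a delay-by-study-day interaction is zero. Dependence appears only on the raw scale. The plan names no transformation, so the raw scale cannot be excluded, but the stronger claim is not established. Confounding of within-arm change with natural course would exist even if everyone entered at the same hour. Nor does the plan say that such change is read as a treatment effect, since it also contrasts the arms at every assessment.

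None of this answers the narrower point: a relevant baseline quantity, tied to an eligibility rule, is absent from the model.

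**Conclusion.** The point holds as one of precision. The documents alone establish that each study day pools 72 hours of the post-injury course and that the model names no adjustment for it. If catecholamines change with time since injury, adjustment would reduce the standard error of a between-arm contrast by about 3 to 14% at half-lives of 2 to 3 days, with residual log-SD 0.5 to 0.8, uniform entry and 25 per arm, analyzed on the log scale. Over half-lives of 1.5 to 5 days the range is about 1 to 22%. The gain shrinks if levels change slowly or entry is less spread out, and it is nil if they do not change. The between-arm contrasts are unbiased as planned. The within-arm contrasts can describe a course but cannot isolate a drug effect. A reader might extend the point to the primary outcome; in-hospital mortality is not part of the study-day model and is not affected.

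**What to change.** 1. Add hours from injury to randomization to the repeated-measures model as a single main-effect covariate. Cost: one degree of freedom.
2. Report the median of those hours by arm.
3. State that conclusions about propranolol and catecholamines rest on the between-arm contrasts, and that within-arm change from SD-1 is descriptive.
4. Do not add a delay-by-study-day interaction. With six sampling times as a factor it would use about five further degrees of freedom, and it is zero under log-scale exponential decline. An analysis indexed by day since injury is at most an optional sensitivity check.

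No new patients, samples or changes in care are needed. Applying the 72-hour rule requires knowing roughly when injury occurred. Exact hours are not among the listed variables, however, so they may have to be extracted from the medical record or trauma registry, which the plan already uses as data sources.

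### Urine sampled during a catecholamine infusion started after randomization could be analysed as the patient's own output, because vasoactive drugs are restricted only at entry

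*Combined protocol and SAP*

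**What the plan says.** The design paragraph names the outcome: "The secondary outcome was to examine the interaction between beta-blockade and catecholamines by measuring urinary catecholamines".

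The eligibility and treatment paragraph mentions vasoactive drugs once, in the list of exclusions: "ongoing resuscitation or vasoactive medications, active acute coronary syndrome". On timing it says "Qualifying patients were randomized within 72 hours of injury", and later "Treatment duration for active study intervention was 14 days with a 48-hour taper of propranolol". The only rule on other drugs after entry concerns additional beta-blockers.

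The variables paragraph sets the sampling: "Urinary catecholamines were collected from discarded urine at study enrollment and then at study day (SD) 2, SD-5, SD-7, SD-10", with a last sample at SD-14 "or when the patient came off study". It gives one reason for dropping a value: "If HCl was not added to the specimen, unpredictable results were obtained", followed by "These values were excluded from analysis". Its list of collected variables has no entry for vasopressors or concomitant drugs.

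The statistical paragraph describes a repeated-measures ANOVA by arm and time. Planned contrasts compare each follow-up with SD-1 and compare the arms at each time. No covariate, flag or sensitivity analysis for infusions is mentioned.

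**The concern.** Norepinephrine, epinephrine and dopamine are given as infusions and are also catecholamines that a urine assay measures. The assay cannot tell infused drug from the patient's own. The stated aim, to study how beta-blockade interacts with catecholamines, makes sense only if the urine value reflects the patient's adrenergic output. The documents do not use the word endogenous, so that reading is inferred from the aim.

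Two planned comparisons are exposed. The between-arm contrasts could reflect a difference in infusion use. The contrasts with SD-1 could reflect infusions started after enrollment, even if use were equal in the two arms. The treatment paragraph foresees low systolic pressure, since it has a rule for holding propranolol, but it does not connect this with urine sampling.

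**Working it through.** **Rules set side by side**

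| Stage | Rule on vasoactive drugs | Rule for dropping a urine value |
|---|---|---|
| Entry, up to 72 hours after injury | Excluded | No acid added |
| SD-2, 5, 7, 10 | None stated | No acid added |
| SD-14 or off study | None stated | No acid added |

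The remark that some values were not physiologically possible is tied to missing acid, so it does not screen out infused drug. Coming off study is undefined and might include starting a vasoactive drug. Even then a sample is taken at that moment, with no rule to discard it. The ANOVA text does not name its variables. I take it to cover the urine values because they are the only measurements with a stated repeated schedule.

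**The plan's own figure.** The only design figure is 99 per group. It cannot be reproduced exactly because base rates are not given; 25% versus 10%, two-sided, gives 100. It does not enter this point.

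**Illustrative size.** The documents give no infusion rate, excreted fraction, urine level or frequency of use. Every input below is an assumption, for norepinephrine only:
- body weight 80 kg, infusion of 0.05 to 0.2 mcg/kg/min for a full day
- 2% to 5% excreted unchanged
- the patient's own urinary output 50 to 300 mcg/day

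1. Infused mass = rate × 80 kg × 1,440 min. This gives 0.05 × 80 × 1,440 = 5,760 mcg/day and 0.2 × 80 × 1,440 = 23,040 mcg/day.
2. Added to urine: 0.02 × 5,760 = 115 mcg/day and 0.05 × 23,040 = 1,152 mcg/day.
3. Fold rise k = 1 + added/own. Low end: 1 + 115/300 = 1.4. High end: 1 + 1,152/50 = 24.
4. With no true difference, the ratio of arm means = [1 + p(k − 1)] / [1 + q(k − 1)], where p and q are the shares of affected samples in the two arms.

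| Shares p, q | k = 1.4 | k = 5 | k = 24 |
|---|---|---|---|
| 10%, 5% | 1.04/1.02 = 1.02 | 1.40/1.20 = 1.17 | 3.30/2.15 = 1.53 |
| 5%, 10% | 1.02/1.04 = 0.98 | 1.20/1.40 = 0.86 | 2.15/3.30 = 0.65 |
| equal | 1.00 | 1.00 | 1.00 |

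The second row is the first with the arms exchanged: the other arm's mean is higher by the same 2% to 53%.

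5. For a contrast with SD-1, equal shares do not cancel. If 10% of follow-up samples and no enrollment samples were affected, the follow-up mean would be multiplied by 1 + 0.10(k − 1), which is 1.04 at k = 1.4 and 3.30 at k = 24. This is the extreme case, because enrollment samples are not guaranteed clean.

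Steps 1 to 3 also assume 24-hour urine. The plan specifies discarded urine and gives no collection interval or reporting unit.

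**The case against.** Several objections stand.

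- No part of the documents says that any patient was infused after entry. A reader might infer from the gap that the urine data are contaminated. The text supports only that they could be.
- A reader might take the enrollment sample as free of infused drug. The exclusion concerns drugs in use at entry, and entry may come up to 72 hours after injury, so a patient whose infusion had just stopped is eligible. The baseline is less likely to be affected, but it is not clean by design.
- A reader might expect more pressure support in the propranolol arm and so a bias in one direction. The documents do not support that. The hold rule works against drug-related low pressure. The exclusions (ongoing resuscitation, current vasoactive use, severe injury elsewhere) select patients with less need of support. An imbalance either way is conjecture.
- The list of variables is worded as what the data included, so it may be incomplete. Vasoactive exposure could have been captured without being listed.
- The trial is a pilot and the outcome is mechanistic. An all-sample comparison fits the stated intent-to-treat analysis.

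These points limit the claim but do not answer it. Even if exposure was recorded, no analysis step uses it, and the one exclusion rule keeps the affected values.

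**Conclusion.** The point holds as a possibility that the plan leaves open. Followed as written, the plan keeps a follow-up value obtained during a catecholamine infusion and compares it as the patient's own output.

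The size and direction are unknown. Under the assumptions shown, with 10% of samples affected in one arm and 5% in the other, the arm means could differ by about 2% to 53% in either direction with no true difference. No single value in that range, such as the 17% at a five-fold rise, deserves preference. If no sample was exposed, the bias is zero and the point is closed.

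Only the urinary catecholamine outcome is concerned, and within it only the analyte that was infused. In-hospital mortality and the sample-size figure do not depend on it.

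**What to change.** 1. From the electronic medical record already used as a data source, record the agent, start and stop of any norepinephrine, epinephrine or dopamine infusion.
2. Flag every urine sample, enrollment included, taken during an infusion or within a fixed window after it, for example 24 hours. Set the window before looking at results by arm.
3. Report flagged counts by arm and study day.
4. Keep the all-sample comparison as the main result. Beside it, show a sensitivity analysis with the infused analyte set to missing in flagged samples and the other analytes kept.

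The cost is one extracted variable and one extra analysis. The second analysis has fewer samples. Flagging is also a post-randomization event that treatment may influence, so that analysis can support the all-sample result but not replace it. The report should say so. No change to treatment is involved.
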